- Process for Aim #3: Patients with ARDS will be analyzed based on hypoxemia conditions (as defined by their PaO₂ to FiO₂ ratio) using 3 classifications: mild (201-300), moderate (101-200), and severe (≤100). This subgroup analysis will evaluate protocol implementation of the high versus low positive end expiratory pressure (PEEP) protocol and assess relationship with patient outcomes. Data from Intermountain ICUs in 2014 have shown that approximately 500 patients meet the criteria for "severe" hypoxemia. Patients with moderate and severe hypoxemia will be identified to determine the frequency of high PEEP protocol usage (which is the recommendation in the protocol). Implementation of the high PEEP protocol will be based upon clinician discretion. We will assess outcomes in the 4 hypoxemia sub-groups noted above using a stratified Kaplan–Meier curve to determine differences in mortality using log rank statistics.
- Hypothesis 3: A high PEEP strategy in patients with moderate to severe hypoxemia and ARDS will improve outcomes.

Specific Aim #4: Measure compliance of the computerized lung protective ventilation protocol after implementation across Intermountain Healthcare's 11

hospitals that manage mechanically ventilated patients with acute respiratory failure.

- Process for Aim #4: Tool utilization and compliance will test the ability
 of a healthcare system to introduce this proven lung protective
 ventilation protocol in a new electronic medical record in a controlled
 clinical environment. To ensure that this is successful, [name] will
 identify local champions to train and educate the healthcare providers.
- Hypothesis 4: Healthcare providers will utilize the computerized ventilation protocol and will comply with protocol instructions.

Study Design:

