This is an observational quality improvement study comparing outcomes before, and after, implementation of a proven lung protective ventilation protocol in an electronic medical record system, iCentra, that will be implemented in phases across Intermountain Healthcare hospitals. A phased implementation with a twomonth washout period will be used to evaluate the primary outcome of interest, ventilator free days (VFDs) to 28 days. Secondary outcomes will include: use of the protocol by clinicians, compliance with protocol instructions, hospital discharge disposition, hospital, 30-day, and 90-day mortality, time to first ICU activity, hospital length of stay, ICU length of stay, heath care utilization, quality of life, and costs of care. As the iCentra electronic medical record is implemented at Intermountain Healthcare hospitals, clinicians will have the opportunity to use the computerized lung protective ventilation protocol, or to order mechanical ventilation settings independently. This is an observational study designed to measure how often the computerized lung protective ventilation protocol will be ordered, compliance with the instructions of the protocol, and clinical outcomes among patients who are managed with the protocol. Physicians may choose to use the protocol on intubated patients requiring mechanical ventilation or they may choose to order other specific mechanical ventilator settings.

A meta-analysis of mechanically ventilated patients without the acute respiratory distress syndrome (ARDS) reported that the cohort who received mechanical ventilation with initial tidal volumes between 6 and 10 ml/kg PBW had mean VFD of 21.9 (SD = 7.8). Using the distribution reported in the meta-analysis as the baseline for an a priori analysis, the current authors demonstrated that 3,900 patients would be sufficient to detect a 1.5-day increase in mean VFD with 80%

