- The risk of this study is a potential loss of confidentiality. The study involves no more than minimal risk to the subject, as the study is observational only and the study will not alter the care that enrolled subjects receive. The computerized lung protective mechanical ventilation protocol will be available to clinicians as an order in iCentra, but will not be required.
- The sample size required to detect a significant change in VFD is estimated to be about 3,900 subjects. Including only the data for which consent can be obtained would prevent accurate conclusions from being drawn.
 Consequently, the research could not practicably be carried out without a waiver of consent.

Waiver of Authorization

PHI will be collected as a part of this study. The PHI will be used only for study purposes and will not be reused or disclosed except as required by law. The information obtained from medical records will be kept separate from clinical records.

All digital study records will be kept within the Intermountain Healthcare firewall in a location that is only accessible to authorized members of the study team. All paper study records will be maintained on a floor with secure badge access that only the research team can access.

After the study is complete, study identifiers will be removed from the dataset.

The data to be collected is detailed below. In particular, the dates to be collected are important for evaluating the primary outcome of interest, VFDs to 28 days.

Data Collection:

Data Elements Extracted from the EDW for the Mechanical Ventilation Study

- Region
- Hospital
- Facility ID
- Account Number
- EMPI
- Admit Date
- Discharge Date
- Admit Year
- Age
- Gender
- ICD Diagnosis code
- ICD Diagnosis description
- ICD Diagnosis long description
- ICU Stay
- Length of Stay(Days)
- Mortality Indicator
- Patient Type(inpatient(I) vs outpatient(O))
- Patient Type(Detailed code)
- Patient Type Description
- Death Location
- Discharge Disposition Description
- Discharge Reason(same as above)
- ED Admit Date
- ED Discharge Date
- Total Cost
- Ventilator Location(First Vent Check Location)
- First Date of Ventilator Check
- Ventilator Mode
- First Date of Ventilator Check
- Intubation Date
- Intubation Location(Same as Ventilator Location)
- Room Trace(It is more detailed than the ones above)
- In Hospital Mortality

- Ventilator Mode
- Machine Corrected Volume
- Set Tidal Volume
- Spontaneous Volume
- Height
- Predicted Body Weight

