- Tidal Volume per Predicted Body Weight
- Measured Volume per Predicted Body Weight
- Difference between Tidal Volume per PBW and Measured Volume per PBW
- Difference between admission date and death date
- 30 Day Mortality
- 60 Day Mortality
- 90 Day Mortality
- Initial Arterial Blood Gas recorded during hospital stay
- PaO2 (measured)
- PaO2 (corrected)
- FiO2
- PaO2 / FiO2

Data Analysis:

Primary Outcomes

The primary outcome will be VFD to day 28. Patients who experience death within 28 days of ICU admission will be counted as having zero VFD.

Secondary outcomes will include: hospital discharge disposition; hospital, 30-day, and 90-day mortality; time to first ICU activity; hospital, ICU length of stay; protocol compliance; implementation of a high PEEP strategy in patients with PaO_2/FIO_2 ratios \leq 200; heath care utilization; quality of life (SF-36 or similar); and costs of care.

Data Analysis

Descriptive analyses will include Fisher's exact test and Pearson's chi-square test for comparing pairs of binomially distributed variables with and without sparse cells, respectively. Wilcoxon rank sum test, a nonparametric analogue of Student's *t* test, will be used to compare non-Gaussian, continuous distributions. Bootstrapped Kolmogorov-Smirnov (K-S) test will compare distributions of

ordinal, discrete data. The bootstrapped K-S test is able to handle instances in which many ties are present between distributions.²⁴

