Generalized linear mixed models (GLMM) with hospital-level random intercepts and an identify link function will be used to measure the effect of initial tidal volume size on VFD. It is proposed to measure the treatment as a continuous variable (rather than as a dichotomous indicator of whether the mechanically ventilated patient was cared for at a post-intervention site) in order to account for the variable "usual care" practices of tidal volume size. The protocol will be phased sequentially in a non-randomized phased implementation manner. Since it is hypothesized that the bundle will improve care and, resultantly, decrease duration of time on ventilator, statistical significance will be determined by a one-tailed, 5% significance test. Heterogeneity among clusters will also be measured and accounted for random intercepts. Potential secular trends will be adjusted for by inclusion of quadratic time effects, which would capture a variety of time effects – from linear to bell-shaped. Patient-specific confounders will be controlled for by additive inclusion of a matrix of patient-level covariates.

Mitigation Plans and Interim Analysis

We plan an interim analysis for futility and efficacy at the end of the third step, following the successful phasing in of the second cluster. If the mean VFD following implementation of the bundle is equivalent to the mean VFD prior to implementation (according to the two one-sided test procedure with 99% confidence having an equivalence margin of four hours) then futility will be declared and further data collection will cease. Conversely, if the mean VFD following implementation has increased by more than 2 days (according to a one-sided hypothesis test with 99% confidence), efficacy will have been established and further data collection will also cease.

Data Sharing:

Development of the ventilation protocol in iCentra for mechanical ventilation will likely increase the number of VFDs, decrease healthcare utilization and decrease cost. To ensure that the proposal deliverables are met, we have designed the following dissemination plan:

Internal Strategic Planning

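### The only acute severity item on the protocol's data list is an oxygenation ratio not tied to intubation, so the promised covariate adjustment can control severity only in part

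*Protocol*

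**What the plan says.** Data Analysis sets out a mixed model with hospital random intercepts and quadratic time. On the exposure it says "It is proposed to measure the treatment as a continuous variable", in place of a before/after indicator. On allocation it says "The protocol will be phased sequentially in a non-randomized phased implementation manner". On confounding it says "Patient-specific confounders will be controlled for by additive inclusion of a matrix of patient-level covariates", and it names no covariate.

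Study Design leaves the exposure to the clinician: "Physicians may choose to use the protocol on intubated patients requiring mechanical ventilation or they may choose to order other specific mechanical ventilator settings".

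Waiver of Authorization introduces the data list with "The data to be collected is detailed below". The baseline items on that list are:
- age, gender, height and predicted body weight;
- "ICD Diagnosis code" with its descriptions, with no field for timing or presence on admission;
- ventilator and intubation location, ventilator mode, and admission and intubation dates;
- "Initial Arterial Blood Gas recorded during hospital stay", with PaO2, FiO2 and their ratio.

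Research Strategy for Specific Aim 4 adds queries for PEEP and other ventilator settings. Specific Aim #3 grades hypoxemia in ARDS by PaO2/FiO2, "using 3 classifications: mild (201-300), moderate (101-200), and severe (≤100)".

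**The concern.** How sick a patient is at intubation plausibly affects both the tidal volume the clinician sets and the VFD that follow. The protocol itself shows one such route. The Significance section lets the attending physician keep patients with raised intracranial pressure off the 6 ml/kg protocol, and these patients may well differ in outcome.

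Hospital intercepts and a quadratic time curve do not remove differences between patients within the same hospital and period. Because the exposure is the patient's own tidal volume, those differences feed directly into the estimate. The covariates are the only safeguard left, and they can be no better than the fields extracted.

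The Significance section also says the population includes patients ventilated for neurologic problems, surgery, overdose or airway protection. In such patients oxygenation is a poor summary of illness. What is at stake is the primary estimate of Aim 1 and its ARDS counterpart in Aim 2.

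**Working it through.** The protocol gives no figure for residual confounding, so there is none to reproduce. The check has two parts.

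**1. The list against what severity adjustment needs**

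| Needed at or before the first tidal volume | On the list? |
|---|---|
| Age, sex, height | Yes |
| Place of start (ED or ICU) | Yes, through ventilator location |
| Oxygenation | Yes, but from the first gas of the stay |
| Blood pressure, heart rate, vasopressor use | No |
| Laboratory values other than the blood gas | No |
| Consciousness score | No |
| Organ-failure or severity score | No |

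The blood gas is defined by the stay, not by intubation. It may come well before intubation in a patient who deteriorates on the ward. It may also come after the first tidal volume has been set, since the ventilator rules call for a ventilator assessment before each blood gas is drawn. For patients intubated on or soon after arrival it may fall close to the right time.

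**2. Size and direction of the remaining bias (illustration)**

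Let S be the severity not captured by the listed covariates, in SD units. Suppose one SD of S changes initial tidal volume by a ml/kg and lowers VFD by b days. Leaving S out shifts the slope of VFD on tidal volume by

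bias = −a × b / SD².

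Inputs:
- SD of tidal volume, from Table 1 with ED and ICU combined. Counts by bin are 8, 27, 568, 1043, 769, 407, 111, 45, 7, 6 and 6, so n = 2,997. Bin midpoints run 3.5, 4.5, … 12.5, 14.5, with 3.5 assumed for the open lowest bin. The mean is 7.02 and the SD 1.27, so SD² = 1.61.
- a = 0.1 to 0.3 ml/kg in absolute value: assumed, not in the protocol. This is a correlation of 0.1/1.27 = 0.08 to 0.3/1.27 = 0.24.
- b = 1 to 3 days: assumed, not in the protocol. Against the protocol's VFD SD of 7.8, S would explain (1/7.8)² = 1.6% to (3/7.8)² = 15% of the variance.

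Results:
- Smallest: 0.1 × 1 / 1.61 = 0.06 day per ml/kg.
- Middle: 0.2 × 2 / 1.61 = 0.25 day per ml/kg.
- Largest: 0.3 × 3 / 1.61 = 0.56 day per ml/kg.

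For scale, a 1.5-day gain from moving the Table 1 mean to the 6 ml/kg target (7.02 − 6 = 1.02 ml/kg, assuming the target is met) is 1.5/1.02 = 1.47 days per ml/kg. The bias is then 0.06/1.47 = 4% to 0.56/1.47 = 38% of the effect sought.

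The sign depends on practice:
- If sicker patients get lower volumes (a negative), the slope moves up. Low tidal volume looks worse than it is, and a true benefit is masked.
- If sicker patients get higher volumes (a positive), the slope moves down, and an apparent benefit is created.

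**The case against.** **The list does hold a severity measure.** PaO2/FiO2 is on it, and the protocol uses it to grade hypoxemia. With age, diagnosis, ventilator location and mode it allows real, if partial, adjustment, and Aim 3 stratifies by it. This stands. A reader might infer that severity cannot be controlled at all, and the document does not support that.

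**The list is not exhaustive.** PEEP, chest radiographs and quality of life are promised elsewhere but do not appear on it, and neither does any date of extubation or unassisted breathing. So absence from the list does not prove that an item will not be collected. But the waiver section presents the list as the data to be collected, and nowhere does the protocol promise a general severity measure, whereas it does promise those other items.

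**The choice of covariates belongs to the SAP.** That is fair as to which covariates enter the model, and the silence on that is not the finding. A SAP cannot adjust for fields that are not extracted, and the list is fixed here.

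**The illustration is assumed and has no fixed sign.** Correct. Under the one-tailed test for benefit, bias that masks benefit cannot produce a false positive. A reader might infer that confounding favours the protocol, but nothing in the document shows the direction. The SD also comes from 2014, before implementation, and the study's own spread may differ.

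**Diagnosis codes.** A reader might infer that the model will adjust for complications caused by ventilation, since the Background section links tidal volume to ARDS and pulmonary infection. No text says that the codes will be covariates, so this is only a conditional caution.

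**Conclusion.** The point holds in a limited form. In a non-randomised comparison with a clinician-chosen exposure, the protocol relies on patient covariates, yet its data list offers one acute severity item, limited to oxygenation and not anchored to intubation. Severity can be adjusted for in part. Haemodynamic, neurologic and other organ dysfunction would be left largely uncontrolled.

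The bias is about 0.06 to 0.56 day per ml/kg in either direction. That range rests on the assumed associations of 0.1 to 0.3 ml/kg and 1 to 3 VFD per SD of uncaptured severity, and on the 2014 spread of tidal volume. It shows scale and does not estimate the bias in this study. The conclusion about the list depends on none of these figures.

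**What to change.** Before extraction begins:

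- Add to the extraction list, and to the data list under the waiver, the routinely charted components of an acute physiology score (vital signs, key laboratory values, vasopressor use, consciousness score), time-stamped at or before the first ventilator check.
- Replace the first blood gas of the stay, for use as a covariate, with the one nearest to intubation and not after it.
- Define every field in the same way in the old and the new record systems.
- Adjust the primary model for the resulting score together with age, sex, height and ED versus ICU start, which is already listed.
- If diagnosis codes are used as covariates, restrict them to those present on admission.

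This needs no new patients or assessments. It does cost extra query and mapping work, on top of what the protocol already expects from the move to iCentra, and an updated waiver list. Some patients will lack components or have no blood gas before intubation, so a rule for missing values is needed. Capture may also differ before and after go-live, in step with the intervention, so completeness and distribution of each field should be compared across the change before the score is used.

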power (*ICC* = 0.10). The team anticipates this study will require a total of 16 months (two months of baseline during which the protocol will not have been implemented at any hospital, eight months of sequentially phasing in the protocol over two-month intervals across four sites along with a two-month washout period, and six months of follow-up once the protocol has been successfully implemented at every site) given that approximately 3,500 patients managed with volume control or pressure control ventilation are admitted each year to the 11 Intermountain hospitals included in this study and each site will not enroll during their two-month washout period, resulting in a total expected enrollment of about 4,000 over 16 months. This proposal will also follow each successive hospital that transitions to iCentra. [name] and his team will make certain that each site is prepared and has been provided the necessary educational materials. [name] will be available for phone consultation from physicians and respiratory therapists for real-time assistance when utilizing the mechanical ventilation protocols.

Collaboration

This research will be conducted with committee identified above, in addition to [name], MD and [name], MD will provide medical oversight. Local site champions have been identified at the 11 hospitals where this protocol will be developed and these healthcare professionals will work closely with [name] and his team.

Background and Significance:

Background

Mechanical ventilation with high tidal volumes may cause mechanical damage to the lung, trigger inflammation, and release cytokines into the systemic circulation. This process may cause fever, leukocytosis, new pulmonary infiltrates, prolong duration of mechanical ventilation, and increase mortality. Lung protective ventilation is an approach that limits tidal volume and distending pressure on the alveolus in order to prevent mechanical ventilation induced volutrauma (damage due to high tidal volume), barotrauma (damage due to high tidal volume).

Lung protective ventilation for patients with the acute respiratory distress syndrome (ARDS) improves outcomes. In a prospective randomized clinical trial

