Those to be enrolled must have respiratory failure requiring intubation and initiation of mechanical ventilation. Patients will be divided into two different groups: those patients who are managed with the computerized lung protective ventilation protocol as ordered by the attending physician and those patients managed with physician specified mechanical ventilation settings.

Compensation

Subjects will not be compensated for participating in this study.

Sample Size

The minimum sufficient sample size to detect a significant change in VFD was computed across a range of effects and heterogeneity. We estimate about 3,900 subjects would be sufficient to detect a 1.5-day increase in mean VFD with 80% power (*ICC* = 0.10) from a baseline of 21.9 VFD (SD=7.8) with a one-tailed test (**Table 3**).

Table 3. Minimum sample size for increase in mean VFD

ICC	1 day	1.5	2 day
		day	
0.01	6,800	3,200	2,300
0.10	8,500	3,900	2,300
0.20	8,300	4,000	2,400

The baseline VFD data for the power analysis was based on reported data from a meta-analysis of the association between tidal volume size and sedation needs

in patients without ARDS²⁵ among those who received initial tidal volumes between 6 and 10 ml/kg PBW – a demographic representative of our study population. The power analyses accounted for expected imbalance of patient enrollment (**Table 4**),^{26,27} heterogeneity among clusters,²⁸ and allowed for a variety of time effects (**Equation 1**).²⁹ This avoided artificial inflation of power at the study design stage.³⁰

The VFD y_{ikt} for each patient were simulated via a linear equation adapted from Hussy *et al.*³¹ with the addition of quadratic time effects:

$$y_{ikt} = \mu + \alpha_k + \beta_1 t + \beta_2 t^2 + \theta x_{ikt} + e_{ikt},$$
 (1)

where μ and e_{ikt} , were derived from the distribution of VFD reported in the metaanalysis by Serpa Neto *et al.*²⁵, θ varied from 1 to 2 per [name]'s instructions, α_k are the hospital-level random intercepts, $\beta = (\beta_1, \beta_2)$ is a vector of quadratic time effects, x_{ikt} is the initial tidal volume size for the *i*th subject in the *k*th cluster at time *t*.

	Volume	Proportion
McKay-Dee	542	0.1584
Utah Valley	608	0.1778
American Fork	68	0.0199
Dixie	479	0.14
Valley View	60	0.0175
IMC	1409	0.4119
LDS	206	0.0602
Riverton	49	0.0143

Table 4. Volume of mechanically ventilated patients in 2014

Methods/Procedures:

Research Strategy for Specific Aims 1 and 2

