Note that although 11 hospitals will be included in the study (IMC, McKay-Dee, Utah Valley, American Fork, Dixie, Valley View, LDS, Riverton), only eight were included in the power analysis because three hospitals (Alta View, Park City, and Logan) were not featured in the baseline data set. The number of mechanically ventilated patients at Alta View, Park City, and Logan is very low, so their expected contribution to patient enrollment would not substantively change the results of the power analysis. These three hospitals will be included in the prospective implementation of a lung protective ventilation protocol for purposes of standardization of care. Critically ill patients with respiratory failure who are intubated at Alta View, Park City, and Logan may have initiation of lung protective mechanical ventilation for management in their ICU, or prior to transfer to an Intermountain tertiary hospital. With a two-month deployment period at each hospital – during which time data will not be collected – a sufficient number of patients could be enrolled in less than 16 months. This corresponds to two months of baseline data collection, eight months of phasing in the protocol, and six months of follow-up once the protocol has been successfully implemented at each of the sites. An example enrollment matrix simulated by a Poisson process is displayed in **Table 5**.

Table 5. 16-month enrollment matrix (n = 4,127)

	NOV	DEC	JAN	FEB	MAR	APR	MAY	JUN	JUL	AUG	SEP	ОСТ	NOV	DEC	JAN	FEB
McKay-Dee	46	39			50	43	55	37	49	50	39	42	52	49	43	61
Utah Valley	52	60	57	57			54	45	72	38	57	54	46	60	48	49
American Fork	8	4	6	10			6	5	4	4	5	6	2	3	10	3
Dixie	45	43	37	34	31	52			33	38	41	43	37	36	47	52
Valley View	3	4	5	6	7	2			7	5	3	4	8	1	5	3
IMC	129	127	116	105	114	130	136	142			115	121	139	120	116	118
LDS	19	19	16	24	17	23	19	12			10	18	17	9	15	15
Riverton	3	3	5	3	1	5	4	5			2	6	7	5	4	1

Risks

The risk of this study is a potential loss of confidentiality, which will be managed as detailed below.

Benefits

This is a quality improvement study evaluating the benefits of a proven lung protective ventilation protocol across Intermountain Healthcare hospitals. Application of the protocol at the discretion of the attending physician to patients with acute respiratory failure requiring intubation and mechanical ventilation is expected to improve outcomes.

Waiver of Informed Consent

This study seeks a waiver of informed consent for these reasons:

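### The interim futility rule (equivalence within four hours at 99% confidence) cannot be met at any size this study can reach

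*Protocol*

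**What the plan says.** The Protocol section on Mitigation Plans and Interim Analysis plans one interim look "for futility and efficacy at the end of the third step, following the successful phasing in of the second cluster". Equivalence of mean VFD before and after implementation is to be judged "according to the two one-sided test procedure with 99% confidence having an equivalence margin of four hours"; if it is shown, "then futility will be declared and further data collection will cease". The test, confidence level, margin, timing and consequence are therefore all fixed in the protocol.

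The figures needed to check the rule are in the same document:

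- **Variability.** Sample Size powers the study "from a baseline of 21.9 VFD (SD=7.8) with a one-tailed test". Table 3 covers ICCs of 0.01, 0.10 and 0.20.
- **Size.** Study Design describes a rollout "resulting in a total expected enrollment of about 4,000 over 16 months". Table 5 is "An example enrollment matrix simulated by a Poisson process" and totals 4,127.
- **Primary model.** Data Analysis says of exposure: "It is proposed to measure the treatment as a continuous variable (rather than as a dichotomous indicator". The primary model's treatment coefficient is thus a slope on tidal volume, not the before/after difference in means that the interim rule names.

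**The concern.** Two one-sided tests declare equivalence only when the whole confidence interval lies inside the margin. If the half-width exceeds the margin, no observed difference can pass, not even zero. Four hours is 0.167 day, about 2% of the 7.8-day SD (0.167/7.8), and an interim early in a study of about 4,000 patients cannot give that precision.

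If so, the protocol states a futility stop that can never operate. A study with no effect would run to full size although the text says it could stop early. The stake is limited: an inert rule does not bias the final estimate or raise the type I error.

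**Working it through.** **Inputs.** SD 7.8 days (Sample Size); margin 4/24 = 0.1667 day; 99% confidence read as one-sided 1% per test, z = 2.326; monthly counts from Table 5, which cover 8 of the 11 hospitals.

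**Reproducing the plan's size.** The Table 5 cells sum to 4,127, as stated. From the annual volume, 3,500 × 16/12 − 3,500 × 2/12 = 4,083, which agrees with about 4,000.

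**When the interim falls.** The third two-month step ends in April of Table 5, with 1,467 patients before and 93 after implementation; the second cluster is then still in its washout. If the look waits until that cluster has post-implementation data, it falls at the end of June, with 1,785 before and 295 after. Complete data are 1,785 and 2,342.

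**Precision required.** Maximum SE = 0.1667/2.326 = 0.0716 day = 1.72 h.

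**Precision available, unadjusted.** SE = 7.8 × √(1/pre + 1/post); half-width = 2.326 × SE × 24.

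| Data | Pre / post | SE (days) | Half-width (h) | Largest SD at which the rule could pass |
|---|---|---|---|---|
| To April | 1,467 / 93 | 0.834 | 46.6 | 0.67 |
| To June | 1,785 / 295 | 0.490 | 27.4 | 1.14 |
| All | 1,785 / 2,342 | 0.245 | 13.7 | 2.28 |
| 4,000 split 1:1, without Table 5 | 2,000 / 2,000 | 0.247 | 13.8 | 2.27 |

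With an observed difference of exactly zero the test statistic is 0.1667/SE = 0.20, 0.34 and 0.68 for the first three rows, against the 2.326 required.

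**Adjusted.** Generalised least squares with a hospital random intercept, a post-implementation indicator and quadratic time, at ICC 0.10, gives SE 1.179, 0.747 and 0.505 day, so half-widths of 65.8, 41.7 and 28.2 h. Over ICC 0.01 to 0.20 the ranges are 60-66, 39-42 and 27-29 h. Without the time terms, complete data give 13.0-14.4 h.

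**Other readings.** A two-sided 99% interval (z = 2.576) is wider: 51.6, 30.3 and 15.2 h. Relaxing to one-sided 5% tests (z = 1.645) still leaves 9.7 h on complete data.

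**Patients needed.**

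- Half-width equal to the margin with a 1:1 split: N = 4 × (7.8 × 2.326/0.1667)², about 47,400, or about 42,700 with hospital variance removed at ICC 0.10 (SD 7.40). At 3,500 a year that is 12 to 14 years, and it passes only if the observed difference is exactly zero.
- 80% chance of declaring equivalence at a true difference of zero: N = 4 × (7.8 × (2.326 + 1.282)/0.1667)², about 114,000.

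**The case against.** *The SD of 7.8 comes from the literature, in patients without ARDS, so the claim is conditional on it.* True, but it would have to fall to 2.28 at full size, or 0.67 to 1.14 at the interim. Deaths within 28 days score zero. With a mean of 21.9, deaths alone give a variance of 21.9² × p/(1 − p), so an SD of 2.28 requires 28-day mortality p of about 1.1% or less, even if every survivor had identical VFD. Covariate adjustment would have to remove about 91% of the variance at full size (1 − (2.28/7.8)²) and 98-99% at the interim.

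*Table 5 is only a simulated example.* Also true. The 1:1 calculation with 4,000 does not use it, and Study Timeline says the three omitted hospitals have very low volume.

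*Little is at stake.* This is the strongest objection, and it stands as a limit on severity. The protocol describes a minimal-risk observational study of records, with the phase-in tied to the iCentra rollout. A futility stop would end data collection and change no patient's care. Deleting the rule would also leave the study without a futility check; it would only make the text honest.

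*The figures for a replacement rule do not describe the planned primary test.* They start from 91% power at 1.5 days, against the 80% stated for about 3,900 patients, and they use a post-implementation indicator, not continuous tidal volume. That stands as a caveat on the replacement's absolute power, but it does not touch the fault in the existing rule.

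**Conclusion.** The futility rule cannot be met. The half-width exceeds the 4-hour margin by a factor of about 3.4 at best (13.7/4, complete data, unadjusted) and by about 7 to 16 at the interim (27.4/4 to 65.8/4). This holds for either interim date, either reading of 99% confidence, every ICC in Table 3, with or without adjustment for hospital and time, and at 95% confidence. The one condition is the protocol's own SD, and no plausible smaller value rescues the rule. The required size is more than ten times what the study expects. It should be fixed because a stated decision threshold is unworkable, although the final estimate and its error rate are unaffected.

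**What to change.** Either change below is enough.

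1. **Delete the equivalence rule.** This costs nothing, because it never triggers, and leaves the protocol openly without a futility stop.
2. **Replace it with a non-binding predictive-power rule** for the before/after difference in mean VFD, from a model adjusted for hospital and time with a post-implementation indicator. State its operating characteristics in the protocol.

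The table gives option 2 on the Table 5 counts at ICC 0.10, with a flat prior and a final one-sided 5% test on the indicator. The information fractions are 0.184 (April) and 0.458 (June), from the squared ratios of the adjusted SEs. Power at a true 1.5 days without a stop is 91%.

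| Stop if predictive power is below | Studies with no effect stopped, April / June | Power at 1.5 days, April / June |
|---|---|---|
| 5% | 22% / 46% | 89.5% / 90% |
| 10% | 33% / 57% | 88% / 89% |
| 20% | 48% / 69% | 84% / 87% |

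If the final SE is instead set to give the protocol's 80% power (1.5/(1.645 + 0.842) = 0.603 day) and the information fractions are kept, the stopping chances under no effect are unchanged. Power becomes about 79% with a 5% cut at either date, and about 73% (April) or 76% (June) with a 20% cut. The loss is therefore about 1 point at a 5% cut and 3 to 7 points at a 20% cut. The loss for the planned test on continuous tidal volume was not calculated and should be simulated before a cut is chosen.

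A futility stop can only remove rejections, so it does not inflate alpha. Neither option needs more patients or data. Widening the margin alone is not a sound repair: even unadjusted, it would have to exceed about 1.1 days (June) to 1.9 days (April), close to or above the 1.5-day target effect.
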